11.1 Adverse Events

Adverse events will be analyzed in terms of treatment-emergent adverse events (TEAEs) which are defined as any AEs that begin or worsen on or after the start of study drug through 63 days after the last dose of IP (i.e., AE start date on or after the first dose date and within last dose date + 63). In addition, an AE that occurs beyond this timeframe and that is assessed by the investigator as possibly related (suspected) to study drug will be considered to be treatment-emergent.

All AEs will be coded using the MedDRA (Version 23.0). The incidence of TEAEs will be summarized by MedDRA SOC and PT. The AE tables will be sorted by SOC and PT (within SOC) in descending frequency within the luspatercept group. If a subject experiences multiple AEs under the same PT (or SOC), then the subject will be counted only once for that PT (or SOC).

The intensity of AEs will be graded 1 to 5 according to the National Cancer Institute Common Terminology Criteria for Adverse Events (CTCAE) Version 4.0. If a subject experiences the same AE more than once with different toxicity grades, then the event with the highest grade will be tabulated in “by grade” tables. In addition, AEs with a missing intensity will be presented in the summary table as an intensity category of “Missing” only if the same event category has no other valid grades.

Tables summarizing the incidence of TEAEs will be generated for each of the following by treatment group (if not otherwise specified, the summary is by SOC and PT):

- TEAEs;
- TEAEs by SOC only;
- Treatment-related TEAEs;
- Serious TEAE;
- Treatment-related serious TEAEs;
- TEAEs by CTCAE maximum severity;
- Treatment-related TEAEs by CTCAE maximum severity;
- TEAE with CTCAE Grade ≥ 3 ;
- Treatment-related TEAE with CTCAE Grade ≥ 3 ;
- TEAEs leading to study drug discontinuation;
- Treatment-related TEAEs leading to study drug discontinuation;
- TEAEs leading to study drug dose reduction;
- Treatment-related TEAEs leading to study drug dose reduction;
- TEAEs leading to study drug dose delay;
- Treatment-related TEAEs leading to study drug dose delay;
- TEAEs leading to death;
- Treatment-related TEAEs leading to death;
- Most frequent TEAEs by PT ($\geq 5\%$ in PT frequency of all subjects or subjects from any treatment group); Most frequent TEAEs by SOC ($\geq 5\%$ in SOC frequency of all subjects); Most frequent TEAEs by SOC and high level term (HLT) ($\geq 5\%$ in HLT frequency of all subjects)
- TEAEs by Age group (≤ 32 years, > 32 years);

- TEAEs by Age group (≤ 32 years, $>32-\leq 50$ years, > 50 years);
- TEAEs by Gender (Male and Female);
- TEAEs by Splenectomy status (Yes/No);

- 
- TEAE by preferred term for QTc Prolongation and Atrial Fibrillation events;
 - All death by cause of death.

Listings for AEs, SAE, and AEs leading to discontinuation will be presented separately. Treatment-emergent AEs will be flagged in the listings. A death listing will be provided for all death events.

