3.2.2 Extended Secondary Objectives

The following secondary objectives will be conducted in this final CSR:

- To evaluate the mean change from baseline in liver iron concentration (LIC) versus placebo up to final database lock
- To evaluate the mean change from baseline in mean daily dose of iron chelation therapy (ICT) used versus placebo up to final database lock
- To evaluate the mean change from baseline in serum ferritin versus placebo up to final database lock
- To evaluate the effect of luspatercept on osteoporosis/osteopenia, total hip and lumbar spine measured by bone mineral density (BMD) versus placebo up to final database lock
- To evaluate mean change from baseline in myocardial iron versus placebo up to final database lock
- To evaluate the effect of luspatercept on healthcare resource utilization versus placebo up to final database lock
- To evaluate the proportion of subjects who are transfusion independent for ≥ 8 weeks versus placebo up to final database lock

- To evaluate the duration of reduction in transfusion burden or transfusion independence up to final database lock
- To evaluate the time to erythroid response up to final database lock
- To evaluate the post-baseline transfusion events frequency versus placebo up to final database lock
- Evaluate the safety of luspatercept versus placebo up to final database lock.

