During the double-blind Treatment Period, subjects received their first subcutaneous (SC) dose of luspatercept or placebo (1 mg/kg) on Day 1 of each dosing cycle. BSC was available to all study subjects, which included RBC transfusions, iron-chelating agents, use of antibiotic therapy, antiviral and antifungal therapy, and/or nutritional support as needed, to minimize the safety risk to subjects. The double-blind Treatment Period lasted up to 48 weeks from study day 1, regardless of dose delays. Upon completion of the 48-week treatment period, subjects could enter the long-term treatment period and continue receiving the investigational product (IP) that they were originally randomized to at the investigator's discretion. The Long-term Treatment Period continued until all subjects completed or discontinued their 48-week treatment period and lasted maximally up to 48 weeks post last subject's first dose or discontinued early, whichever occurred first. Treatment was administered every 21 days (3 weeks) during the Treatment Period and during the Long-term Treatment Period, unless dose delay or treatment discontinuation was indicated. Subjects randomized to the luspatercept group started luspatercept at 1 mg/kg dose level and could be dose titrated up to a maximum of 1.25 mg/kg.

Upon last subject completing 48 weeks after first dose date, the study was unblinded. Placebo subjects who were still ongoing or in follow-up had to fulfill eligibility criteria and opted to receive

luspatercept in the Open-label Phase or to discontinue treatment and enter the Post-treatment Follow-up Period. In the Open-label Phase, subjects may receive luspatercept until all subjects initially assigned to luspatercept in the double-blind Treatment Period complete the total treatment duration of 5 years from subjects' Dose 1 Day 1 or discontinue early. The Open-label Phase was monitored by an independent external DMC.

All subjects who discontinue treatment will undergo a 156-week Post-treatment Follow-up Period, following the last dose of IP (monitored at week 9, week 24, and every 24 weeks until week 144) and then the end of study visit at week 156. Specifically, discontinued placebo subjects may have several follow up visits before unblinding and re-enter the treatment in Open-label Phase. Subjects who stay on treatment until end of the Open-label Phase will enter the end of study visit directly.

[figure not shown]

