11. SAFETY ANALYSIS

The purpose of this section is to define the safety parameters for the study. All summaries of safety data will be conducted using the safety population. The safety analysis includes adverse events (AEs), clinical laboratory tests, vital signs, electrocardiogram (ECG), cardiac Doppler or Multi Gated Acquisition Scan (MUGA), and antidrug antibody (ADA) testing. In addition, pregnancy test and menstrual status assessments will be provided for female subjects.

If not otherwise specified (for example, AEs), safety summaries will use all collected records including data collected after the primary database lock. The safety analyses will be summarized by the following treatment groups:

- Luspatercept excluding cross-over: original luspatercept patients
- Placebo: original placebo patients
- Luspatercept cross-over only: original placebo patients who crossed over to luspatercept
- Luspatercept including cross-over: all the patients who took luspatercept in DB and/or OL periods.

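### Final-CSR adverse event tables give crude percentages over unequal time at risk, so for events that accrue over time they do not estimate luspatercept-versus-placebo safety

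*SAP*

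**What the plan says.** The final-CSR safety objective in SAP 3.2.2 is comparative: "Evaluate the safety of luspatercept versus placebo up to final database lock".

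SAP 11.1 describes the tables: "The incidence of TEAEs will be summarized by MedDRA SOC and PT". A subject with repeated events under a term counts once for it, whatever the time observed. An event is treatment-emergent from first dose "through 63 days after the last dose of IP", or later if the investigator suspects a relation to study drug. The list covers all, serious and grade 3 or higher events. SAP 11.2 (malignancy, premalignant conditions) and 11.3 (embolic and thrombotic events) also summarise by preferred term.

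SAP 11 sets four groups. The first is "Luspatercept excluding cross-over: original luspatercept patients". The others are original placebo, cross-over subjects only, and everyone who took luspatercept.

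On exposure, SAP 4.1 lets open-label treatment run until all subjects first assigned to luspatercept "complete the total treatment duration of 5 years" or stop early. Placebo treatment ends at unblinding, when the last subject reached 48 weeks.

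Time at risk is handled in only two places: a descriptive treatment-duration summary (SAP 9.1), and for bone pain a split at 24 weeks with time to first event (SAP 11.3).

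**The concern.** A crude percentage rises with the length of observation. If one group is observed two to three times as long as another, an event that arrives steadily will show a higher percentage there even when the drug does nothing. The events this affects most are those that matter for long-term safety, such as malignancy and thromboembolism.

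The SAP deals with the same imbalance for efficacy. Section 10 cuts placebo assessments at cross-over, and 10.5.2 limits placebo liver iron to Weeks 24, 48 and 96. Neither step is written for adverse events. A reader who uses the final tables to answer the 3.2.2 objective could take a difference in follow-up for a difference in toxicity.

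**Working it through.** The documents give no person-time total or expected event percentage, so there is no planned figure to reproduce. The check bounds exposure from their dates and then asks what the crude tables would show if the two arms had the same true rate.

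**Exposure bounds**
- Earliest first dose: protocol issued 25 August 2015 (SAP 2) plus a run-in of at least 12 weeks, so 17 November 2015.
- Latest first dose: 48 weeks before the 11 May 2018 data cutoff (SAP 2, 5.1), so 9 June 2017. This agrees with the June 2017 target for closing randomisation in the protocol's amendment justification, 1.7.6.
- Placebo, if treated to 11 May 2018 (used as a stand-in for unblinding): 48 to about 129 weeks.
- Luspatercept, if still treated at SAP approval on 12 March 2021, which is 148 weeks later: 48 + 148 = 196 weeks at least, capped at 5 years (about 260 weeks).

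The SAP expects exposure of this length. Its intervals run to Week 228 (5.1), and its top dose-count category is more than 64 doses (9.2), or over 64 × 3 = 192 weeks.

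**Formula.** Crude incidence = 1 − exp(−rate × time at risk), with the same constant rate in both arms.

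**Check at the mean, no discontinuation.** Uniform entry gives means of 88.7 weeks (placebo) and 235.0 weeks (luspatercept). At 0.10 per year:
- placebo: 1 − exp(−0.10 × 88.7/52.18) = 15.6%
- luspatercept: 1 − exp(−0.10 × 235.0/52.18) = 36.3%

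**Simulation.** This used 1,000,000 subjects per arm, uniform entry, the same assumed discontinuation rate in both arms, and 9 weeks of window after discontinuation. Cells show placebo / luspatercept.

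| Discontinuation per year | Mean weeks at risk | Ratio | Crude % at 2 per 100 PY | Crude % at 10 per 100 PY | Exposure-adjusted rate when truth is 10 |
|---|---|---|---|---|---|
| 0 | 88.7 / 235.0 | 2.65 | 3.3 / 8.6 | 15.5 / 36.2 | 10.0 / 10.0 |
| 10% | 82.5 / 192.2 | 2.33 | 3.1 / 7.1 | 14.5 / 30.1 | 10.0 / 10.0 |
| 20% | 77.0 / 159.8 | 2.08 | 2.9 / 5.9 | 13.6 / 25.5 | 10.0 / 10.0 |
| 40% | 67.7 / 116.1 | 1.72 | 2.6 / 4.3 | 12.0 / 19.1 | 10.0 / 10.0 |

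SAP 11.1 also lists the most frequent terms with a crude 5% cut-off. At 2 per 100 person-years in both arms and discontinuation of 0 to 20%, luspatercept passes that cut-off and placebo does not.

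**Opposite case: early events only.** Suppose 20% of subjects in each arm have a first event at 0.1 year and nobody has one later. Crude incidence is correctly 20% in both. With the no-discontinuation means (1.70 and 4.50 years), the exposure-adjusted rates are:
- placebo: 0.20 / (0.20 × 0.1 + 0.80 × 1.70) = 0.20/1.38 = 14.5 per 100 person-years
- luspatercept: 0.20 / (0.20 × 0.1 + 0.80 × 4.50) = 0.20/3.62 = 5.5 per 100 person-years

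For such events the adjusted rate is the misleading measure, so neither measure is enough alone.

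**The case against.** The strongest reply is that a randomised comparison with equal planned follow-up already exists. SAP 3.2.1 lists safety versus placebo before the primary lock as completed. SAP 4.1 says the primary CSR's plan covered data up to unblinding, and SAP 2 says those results are carried into the final CSR without update. Until unblinding both arms followed the same schedule. This stands: a reader might infer that no equal-follow-up comparison exists anywhere, and the documents do not support that. It also argues against cutting the comparison at 48 weeks, because that would discard blinded data from the Long-term Treatment Period. It does not rescue the final tables, since SAP 3.2.2 sets a separate comparative objective up to final lock.

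Other points also stand in part:
- A reader might take SAP 11's sentence on data span as governing the adverse event tables. It reads "If not otherwise specified (for example, AEs), safety summaries will use all collected records including data collected after the primary database lock", so adverse events are its own example of an exception. The longer span comes from the treatment-emergent window in 11.1 and the extended endpoint in 4.2.4.2.
- A reader might infer that luspatercept will look worse on every event. That fails for early-onset events, as the working shows.
- No adverse event test is planned, so the harm is to interpretation and not to a decision rule.
- One bullet in the 11.1 list is blank and SAP 15.2 is partly redacted. An exposure-adjusted table hidden by redaction cannot be ruled out.
- SAP 11 gives no cut-off for the placebo column. A cut at cross-over has to be inferred from the separate cross-over group and the as-received rule in 5.2.2. If events after cross-over stayed under placebo, the exposure gap would shrink, but that column would then hold events that occurred on luspatercept.

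**Conclusion.** The concern holds for events that accrue over time. On the visible text, the final-CSR percentages in SAP 11.1 to 11.3 do not estimate the luspatercept-versus-placebo contrast up to final lock. At an equal true rate of 10 per 100 person-years they would show about 12 to 16% on placebo and 19 to 36% on luspatercept. The direction was the same in every scenario run. For events confined to the first months the bias is near zero.

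The size rests on assumptions that the documents do not supply: uniform entry, equal discontinuation of 0 to 40% per year in both arms, a constant event rate, 11 May 2018 as the end of placebo treatment, SAP approval as the end of luspatercept data, and placebo time cut at cross-over. The primary CSR is much less affected.

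**What to change.** 1. Keep the crude tables. For all, serious and grade 3 or higher TEAEs, embolic/thrombotic events and malignancy/premalignancy, add exposure-adjusted incidence for each of the four groups: subjects with a first event per 100 person-years at risk, with 95% CI.
2. State for safety, as SAP 10 does for efficacy, that placebo events and person-time stop at the first open-label luspatercept dose. This also settles the overlap when a subject crosses over within 63 days of the last placebo dose.
3. Base the randomised luspatercept-versus-placebo safety comparison on the whole double-blind period up to unblinding (Treatment plus Long-term Treatment Periods), as in the primary CSR. Label the post-unblinding columns as non-comparative.
4. Add a note that the rates assume a roughly constant hazard and should be read beside the crude tables for early-onset events.

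Cost: no new data. First-dose, last-dose and event start dates are already needed for SAP 9.1 and 11.1. Person-time to first event has to be derived separately for each term, which is modest extra programming.

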11.2 Adverse Events of Special Interest (AESI)

The following adverse events are of special interest:

- Malignancy
- Premalignant Conditions

An AESI summary by PT terms will be provided for TEAEs by treatment group. A listing for AESI will be provided as support.

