**Table 2: Study Endpoints**

Endpoint	Name	Description	Time of Endpoint Measurement			Timeframe
			24 weeks	48 weeks	Long -Term	
Primary Endpoint	
 
Proportion of subjects with hematological improvement, defined as <math>\geq 33\%</math> reduction from baseline in RBC transfusion burden with a reduction of at least 2 units from Week 13 to Week 24 compared to the 12-week interval prior to randomization for luspatercept plus BSC versus placebo plus BSC.
 
	Number of RBC units transfused from Week 13 to Week 24, and in the 12 weeks prior to randomization	X	-	-	12 weeks prior to randomization; Week 13-Week 24.
Safety Endpoints	
 
Safety, including:                             
 
Type, frequency, and severity of adverse events and relationship to luspatercept (per NCI CTCAE version 4.0)
 
 
 
	Frequency/severity of adverse events	X	X	X	All AE Dose 1 Day 1 through up to 9 weeks post last dose. Only related AEs from week 9 until End of Study.
	
 
Frequency of antidrug antibodies [REDACTED]
 
	ADA measurements; [REDACTED]	X	X	X	Dose 1 Day 1 through up to 2 years
Secondary Efficacy Endpoints	
 
Proportion of subjects with hematological improvement, defined as <math>\geq 33\%</math> reduction from baseline in RBC transfusion burden with a reduction of at least 2 units from Week 37 to Week 48 compared to the 12-week interval prior to randomization for luspatercept plus BSC versus placebo plus BSC.
 
	Number of RBC units transfused from Week 37 to Week 48, and in the 12 weeks prior to randomization	-	X	-	12 weeks prior to randomization; Week 37-Week 48

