All AEs regardless of causality will be recorded by the Investigator from the time the subject signs informed consent until 9 weeks after the last dose of IP as well as those SAEs made known to the Investigator at any time thereafter that are suspected of being related to IP. In addition, AEs that are suspected to be related to the IP as well as new malignancies or pre-malignancies regardless of causality (see Section 10.5.2) will be recorded by the Investigator until 156 weeks after the last dose of IP. Information will be collected as described in the Table of Events, Table 3 and Section 6.6. AEs and SAEs will be recorded on the AE page of the eCRF and in the subject's source documents. All SAEs must be reported to Celgene Drug Safety within 24 hours of the Investigator's knowledge of the event by facsimile, or other appropriate method, using the SAE Report Form, or approved equivalent form.

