### 10.5.2. Malignancy and Pre-malignancy Reporting

The occurrence of a new malignancy or pre-malignant lesion will be monitored as an event of interest and should be included as part of the assessment of adverse events throughout the course of the study. Investigators are to report the development of any new malignancy or pre-malignant lesion as a serious adverse event, regardless of causal relationship to IP, occurring at any time for the duration of the study, from the time of signing the ICF up to and including 156 weeks of follow-up.

Events of new malignancy or pre-malignant lesions (excluding benign tumors or benign neoplasia) are to be reported to Celgene Drug Safety within 24 hours of the Investigator's knowledge of the event by facsimile, or other appropriate method, using the SAE Report Form, or approved equivalent form and must be considered an "Important Medical Event" even if no other serious criteria apply; these events must also be documented in the appropriate page(s) of the CRF and subject's source documents. Documentation of the diagnosed malignancy must be provided at the time of reporting as a serious adverse event (eg, any confirmatory histology or cytology results, x-rays, CT scans, etc.).

Malignancies or cancerous tumors are lesions capable of invading into adjacent tissues, and may be capable of spreading to distant tissues. A benign tumor has none of those properties.

Malignancy or cancer is characterized by anaplasia, invasiveness, and metastasis.

Pre-malignant or precancerous lesions refer to a state of disordered morphology of cells that is associated with an increased risk of cancer. If left untreated, these conditions may lead to cancer. Such conditions are usually either dysplasia or benign neoplasia (and the dividing line between those is sometimes blurry). Sometimes the term "precancer" is used to describe carcinoma in situ, which is a noninvasive cancer that has not progressed to an aggressive, invasive stage. Not all carcinoma in situ will progress to invasive disease.

Pre-malignant lesions are morphologically atypical tissue which appears abnormal under microscopic examination, and in which cancer is more likely to occur than in its apparently normal counterpart.

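### The only by-arm table of malignancy and premalignant conditions stops at 63 days off drug unless the investigator suspects the drug, although the protocol records all such cases for 156 weeks

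*SAP*

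**What the plan says.** **Collection.** Protocol Section 10.1 says that "new malignancies or pre-malignancies regardless of causality (see Section 10.5.2) will be recorded by the Investigator until 156 weeks after the last dose". Section 10.5.2 makes every such case a serious adverse event and sets the period as "from the time of signing the ICF up to and including 156 weeks of follow-up". Section 6.6 and Table 3 require the investigator to see subjects at least every 24 weeks to look for them.

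**Analysis.** SAP Section 11.2 provides one summary of these events: "An AESI summary by PT terms will be provided for TEAEs by treatment group". A supporting listing is also planned. SAP Section 11.1 defines TEAEs as "any AEs that begin or worsen on or after the start of study drug through 63 days after the last dose of IP", and adds later events only if the investigator suspects the study drug.

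The general rule in SAP Section 11 does not widen this, because it names AEs as an exception: "If not otherwise specified (for example, AEs), safety summaries will use all collected records including data collected after the primary database lock". One item in Section 11.1 is not restricted to TEAEs: "All death by cause of death".

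**A related mismatch.** The safety endpoint timeframe in Protocol Table 2 reads "Only related AEs from week 9 until End of Study". That may be where the SAP rule comes from, but for these two event types it does not agree with Protocol Sections 10.1 and 10.5.2.

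**The concern.** The protocol gives malignancy and pre-malignancy a collection window of their own, three years long and independent of the causality assessment. The table that reports them uses the ordinary adverse-event window, which ends after nine weeks and reopens only on a judgement of relatedness. Causality is thus kept out of collection and then decides whether a late case is counted.

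These are the only two events of special interest in the SAP. With rare events, one or two uncounted cases can change how a by-arm comparison reads. The table also shows no person-time, although placebo subjects may cross over at unblinding while luspatercept treatment can run to five years. Crude percentages can then differ between groups with equal true rates.

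The 156-week follow-up may have been introduced because of malignancy, but the rationale is redacted and the argument does not depend on it.

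**Working it through.** **1. The windows.** The SAP's 63 days equals the protocol's nine-week all-causality AE period: 9 × 7 = 63. Malignancy follow-up is 156 × 7 = 1092 days off drug. Counted irrespective of causality: 63/1092 = 5.8%. Not counted unless suspected: 1092 − 63 = 1029 days (147 weeks), or 94.2%.

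**2. Where each case is counted.**

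| Case | By-arm count |
|---|---|
| Onset from first dose to last dose + 63 days | AESI table |
| Later onset, suspected | AESI table |
| Later onset, not suspected, fatal | Deaths by cause |
| Later onset, not suspected, non-fatal | None visible; AE and SAE listings, probably the AESI listing |

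The listings flag TEAEs, which implies that they also contain non-TEAEs. Section 11.2 does not say so for the AESI listing.

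**3. Person-time outside the table.** From the documents: 200 luspatercept subjects (SAP Section 4.4), and Week 228 as the end of the last transfusion interval in SAP Section 5.1. Subjects treated to the end contribute no off-drug follow-up: "Subjects who stay on treatment until end of the Open-label Phase will enter the end of study visit directly". Assumed: Week 228 as the end of observation; 30% (60) discontinue, uniformly over Weeks 24 to 228; 0.3 to 1.0 not-suspected events per 100 person-years (PY).

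- *Follow-up cut at Week 228.* For leaving week L, uncounted weeks are max(0, min(156, 228 − L) − 9). The mean is (48 × 147 + 147²/2)/204 = 17,860.5/204 = 87.6 weeks. Total: 60 × 87.6 × 7/365.25 = 101 PY, giving 0.3 to 1.0 events.
- *Full 156 weeks for each discontinuer.* 60 × 1029/365.25 = 169 PY, giving 0.5 to 1.7 events.
- *Time the table covers.* (140 × 228 + 60 × (126 + 9)) × 7/365.25 = 767 PY, where 126 is the mean leaving week.
- *Share outside.* 101/(101 + 767) = 12% to 169/(169 + 767) = 18%.
- *Upper bound, all 200 followed off drug for 156 weeks.* 200 × 1029/365.25 = 563 PY, giving 1.7 to 5.6 events.

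**4. Effect of no person-time.** Crude incidence is 1 − exp(−rate × time). Assume the same true rate in both groups and 72 weeks (1.38 years) on placebo. For luspatercept, 70% run to Week 228 and 30% leave uniformly over Weeks 24 to 228.

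| Rate per 100 PY | Placebo | Luspatercept |
|---|---|---|
| 0.3 | 0.4% | 1.1% |
| 1.0 | 1.4% | 3.7% |

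**The case against.** The strongest reply is that the SAP does what the protocol's analysis section asks. Protocol Section 9.7 promises TEAE summaries, while Sections 10.1 and 10.5.2 govern recording and reporting. The amendment rationale ties nine weeks to five half-lives, after which no drug effect is expected. Little is hidden either: suspected and fatal late cases are tabulated, the rest can be read in listings, and the expected number is one or two at most under the main assumptions. This stands as a reason to call the problem moderate. It does not settle the point, because the half-life argument supports the window for general AEs, whereas the protocol set a separate window for these two event types. A listing gives neither denominator nor rate.

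The magnitude is also open to challenge. The 169 PY figure ignores the roll-over lock, and even 101 PY assumes no loss among discontinuers. If half left follow-up at once, about 50 PY and 0.15 to 0.5 events would remain. Discontinued luspatercept subjects who are re-dosed in the Open-label Phase have a later last dose, so gap events may fall inside the window. These points are fair; the figures are illustrations, not forecasts.

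Post-treatment placebo time falls largely before unblinding, so the late comparison will be thin. The unequal-exposure example is a separate weakness from the TEAE cut-off, and it makes luspatercept look worse rather than better. Both are true; the same table with person-years answers both.

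Finally, part of the SAP is redacted, so the absence of a table can be asserted only for the visible text. The one blank item in Section 11.1 sits under the heading for TEAE incidence tables. Other routes to a count, such as a wholly missing onset date or a hematological malignancy recorded as the reason for stopping treatment, are narrow.

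**Conclusion.** The concern holds. Followed as written, the SAP gives a by-arm count of its two events of special interest that is incomplete after Day 63 off drug, and late inclusion depends on a causality opinion. On-treatment time, suspected late cases and fatal cases are covered.

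Under the stated assumptions the gap is about 12% to 18% of luspatercept observation time, or 0.3 to 1.7 events, and less with attrition. The discontinuation pattern, end of observation, placebo duration and event rates are all assumed; only the 63-day and 156-week windows and the 200 subjects come from the documents. No efficacy result depends on this table. It should be fixed, because the rule as stated yields the wrong count for these events and the remedy is small.

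**What to change.** - Add one AESI table of all malignancy and pre-malignancy events from first dose to the end of available follow-up, irrespective of causality and TEAE status, by the treatment groups in SAP Section 11.
- Show subjects with events, person-years and rate per 100 person-years, split into on-treatment (to last dose + 63 days) and post-treatment. End placebo time at the first luspatercept dose.
- State that the AESI listing covers all events, not only TEAEs, and keep the planned TEAE table as a secondary display.
- Note that these two event types follow the all-causality window of Protocol Sections 10.1 and 10.5.2, not the related-only timeframe in Table 2.

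The cost is one table and a few sentences, with no new data. The reported number of malignancies may rise, and rates based on few events will be imprecise.
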